**3.2. Secondary Endpoints****Immunogenicity**

Immunogenicity with respect to the components of the investigational vaccine before and 1 month after booster vaccination with MenACWY-TT vaccine:

- Percentage of subjects with rSBA-MenA, rSBA-MenC, rSBA-MenW-135 and rSBA-MenY titers  $\geq 1:8$ ,  $\geq 1:128$ , and GMTs.
- Percentage of subjects with anti-TT concentrations  $\geq 0.1$  IU/mL,  $\geq 1.0$  IU/mL, and GMCs.

**Safety and reactogenicity**

- Occurrence of solicited local and general events within 4 days (Day 0 to Day 3) after MenACWY-TT booster vaccination.

- Occurrence of unsolicited adverse events (AEs), within 31 days (Day 0 to Day 30) after MenACWY-TT booster vaccination.
- Occurrence of SAEs, Guillain-Barré syndrome (GBS) and new-onset chronic illnesses (NOCI) (eg, asthma, autoimmune disorders, type I diabetes, allergies) within 31 days (Day 0 to Day 30) after MenACWY-TT booster vaccination.
- Occurrence of SAEs related to primary vaccination and any event related to lack of vaccine efficacy (ie, meningococcal disease) from the subject’s last visit in the primary study MenACWY-TT-036 or in the persistence study MenACWY-TT-043 EXT:036 Y2, 3, 4, 5 until entry in Study C0921005 (MenACWY-TT-101 EXT:036 Y10).

The intensity of the solicited events will be assessed as described in Table 2:

**Table 2. Intensity Scales for Solicited Events**

Adverse Event	Intensity grade	Parameter
Pain at injection site	0	None
	1	Mild: Any pain neither interfering with nor preventing normal every day activities.
	2	Moderate: Painful when limb is moved and interferes with every day activities.
	3	Severe: Significant pain at rest. Prevents normal every day activities.
Redness at injection site		Record greatest surface diameter in mm
Swelling at injection site		Record greatest surface diameter in mm
Fever*		Record temperature in °C
Headache	0	Normal
	1	Mild: Headache that is easily tolerated
	2	Moderate: Headache that interferes with normal activity
	3	Severe: Headache that prevents normal activity
Fatigue	0	Normal
	1	Mild: Fatigue that is easily tolerated
	2	Moderate: Fatigue that interferes with normal activity
	3	Severe: Fatigue that prevents normal activity
Gastrointestinal symptoms (nausea, vomiting, diarrhea, and/or abdominal pain)	0	Gastrointestinal symptoms normal
	1	Mild: Gastrointestinal symptoms that are easily tolerated
	2	Moderate: Gastrointestinal symptoms that interfere with normal activity
	3	Severe: Gastrointestinal symptoms that prevent normal activity

\* Fever is defined as temperature  $\geq 37.5^{\circ}\text{C}$  for oral, axillary or tympanic route, or  $\geq 38.0^{\circ}\text{C}$  for rectal route. The preferred route for recording temperature in this study will be oral.

The maximum intensity of local injection site redness/swelling will be graded as follows:

Grade	Intensity
0	None
1	>0 - ≤20 mm
2	>20 - ≤50 mm
3	>50 mm

The maximum intensity of fever from the oral/axillary or tympanic routes will be graded as follows:

Grade	Intensity
0	<37.5°C
1	≥37.5°C - ≤38.5°C
2	>38.5°C - ≤39.5°C
3	>39.5°C

Temperatures obtained via the rectal route will be adjusted to the same scale by subtracting 0.5°C.

Subjects will be summarized by the maximum intensity over Days 0-3.

The intensity of the unsolicited AEs will be assessed as described below:

1 (mild) = an AE which is easily tolerated by the subject, causing minimal discomfort and not interfering with everyday activities.

2 (moderate) = an AE which is sufficiently discomforting to interfere with normal everyday activities.

3 (severe) = an AE which prevents normal, everyday activities. Such an AE would, for example, prevent attendance at work/school and would necessitate the administration of corrective therapy.

The investigator will assess the maximum intensity that occurred over the duration of the event for all unsolicited AE (including SAE).

Each solicited event and unsolicited AE will have an assigned causality:

All solicited local (injection site) events will be considered causally related to vaccination. The investigator is obligated to assess the relationship between investigational

vaccine/product and the occurrence of each unsolicited AE (including SAE) and for general solicited events.

### 3.3. Baseline Variables

Baseline variables will include sex, race, age at primary vaccination, age at booster vaccination, and elapsed years from primary vaccination to booster vaccination. Elapsed years will be calculated as [date of booster vaccination minus date of primary vaccination + 1]/365.25, rounded down to the nearest tenth decimal place.

## 4. STUDY POPULATION

### 4.1. Booster Total Vaccinated Cohort (TVC)

The booster TVC for safety will include all vaccinated subjects in Study MenACWY-TT-036 with a MenACWY-TT booster vaccine administration documented.

For the analysis of immunogenicity after the booster vaccination the booster TVC will include all subjects for whom data concerning immunogenicity endpoint measures after the booster vaccination are available.

### 4.2. Booster According-to-Protocol (ATP) Cohort for Safety

The booster ATP cohort for safety will include all subjects:

- who meet all inclusion criteria and no exclusion criteria for the study.
- who received a dose of study vaccine MenACWY-TT or Mencevax ACWY in Study MenACWY-TT-036.
- who received a MenACWY-TT booster dose.
- who had a known administration site for the booster vaccine.
- who did not receive a vaccine not specified or forbidden in the protocol (subjects who received a vaccine not foreseen by the study protocol 30 days after the study vaccine dose will be eliminated from the booster ATP cohort for safety if the vaccine not foreseen by the protocol was administered before the postvaccination blood sample).
- who were not excluded from the ATP cohort for persistence at Month 120, unless the reason for exclusion was either noncompliance with the protocol-defined serum sampling windows or a lack of availability of immunogenicity results at Month 120 (prebooster vaccination).

No analyses using the booster ATP cohort for safety are proposed. However, this cohort helps define the booster ATP cohort for immunogenicity.

**4.3. Booster ATP Cohort for Immunogenicity**

The booster ATP cohort for immunogenicity will include subjects:

- who meet requirements of the booster ATP cohort for safety.
- who comply with procedures defined in the protocol including meeting visit interval from primary vaccination in Study MenACWY-TT-036 to booster vaccination: 520 ±26 weeks, inclusive.
- who comply with procedures defined in the protocol including meeting blood sampling intervals from Visit 1 to Visit 2: 21-48 days, inclusive.
- who have assay results available for antibodies against any study vaccine antigen for the blood sample taken 1 month after booster vaccination at Month 121, and
- who were not administered a vaccine not foreseen by the study protocol before the post-booster vaccination blood sample. Other restrictions may apply (see [Section 4.6](#)).

**4.4. Total Cohort at Month 120**

The total cohort at Month 120 will include all vaccinated subjects from the vaccination stage of Study MenACWY-TT-036 who return for the Month 120 follow-up, ie, subjects who were vaccinated in MenACWY-TT-036 and returned for Month 120 visit.

For the analysis of persistence, the total cohort at the Month 120 visit will be further restricted to vaccinated subjects for whom data concerning persistence endpoint measures are available, ie, at least 1 titer at Month 120 visit.

**4.5. ATP Cohort for Persistence at Month 120**

The ATP cohort for antibody persistence for the Month 120 visit will include all evaluable subjects:

- who were eligible in Study MenACWY-TT-036.
- who received the primary vaccination with MenACWY-TT or Mencevax ACWY during Study MenACWY-TT-036.
- who had assay results for at least one tested antigen at Month 120.
- who did not receive a meningococcal vaccine not planned in Study MenACWY-TT-036 before Month 120 visit.

- who did not have a history of meningococcal group A, C, W-135, or Y disease prior to Month 120 visit.
- who complied with the blood sampling interval ( $520 \pm 26$  weeks, inclusive from primary vaccination in Study MenACWY-TT-036 at Month 120).
- who did not have an immunocompromising medical condition.
- who did not receive any immunosuppressant(s) or other immune-modifying drug(s), immunoglobulins, any blood products, investigational drugs, and/or investigational vaccines during the timeframe specified in the protocol.
- who were not excluded from the ATP cohort for immunogenicity in the primary Study MenACWY-TT-036, and/or from the previous ATP persistence cohorts, unless the reason for exclusion was either noncompliance with the protocol-defined serum sampling windows or a lack of availability of immunogenicity results at previous time point.

Other restrictions may apply (see Section 4.6).

#### **4.6. Possible Additional Restrictions on Booster ATP for Immunogenicity and ATP for Persistence at Month 120**

The use of concomitant medications/products/vaccines discussed in Section 6.5.2 of the protocol may also exclude a subject from the booster ATP cohort for immunogenicity. The use of the following concomitant medications/products/vaccines may determine a subject's inclusion in the ATP analysis.

- Any investigational or non-registered product (drug or vaccine) other than the study vaccine used during the study period.
- Immunosuppressants or other immune-modifying drugs administered chronically (ie, more than 14 days in total) during the study period. For corticosteroids, this will mean prednisone  $\geq 0.5$  mg/kg/day with an upper limit of 10 mg/day or equivalent. Inhaled, topical, and intra-articular steroids are allowed.
- A vaccine not allowed by the study protocol but administered during the period starting 30 days before the booster dose of vaccine and ending 30 days after, with the exception of inactivated influenza vaccine which can be administered at any time during the study according to the local recommendations.
- Administration of a meningococcal vaccine not allowed by the study protocol at any time during the study period.

- Immunoglobulins and/or any blood products administered within the 3 months preceding the study vaccination or planned administration during the study (ie, between Visit 1 and Visit 2).

The following intercurrent medical conditions may result in the elimination of subjects from the ATP cohort for immunogenicity:

- Occurrence of meningococcal disease.
- Any confirmed or suspected condition that has the capability of altering the subject's immune response (eg, intercurrent lymphopenia).
- Any confirmed or suspected immunosuppressive or immunodeficient condition based on medical history and physical examination (no laboratory testing required).

A detailed, comprehensive list of reasons for elimination from ATP analyses will be established at the time of data cleaning.

#### **4.7. Adapted ATP Cohort**

The adapted ATP cohort will denote, for each time point, subjects belonging to the corresponding ATP cohort for immunogenicity (Month 0 and Month 1) or persistence (all other months) for that time point.

The blood sampling intervals are 21 to 48 days for Month 1; 96 to 112 weeks for Month 24; 148 to 164 weeks for Month 36; 200 to 216 weeks for Month 48; 252 to 268 weeks for Month 60; and 494 to 546 weeks for Month 120.

The adapted ATP cohort will be used for the modeling prediction analysis ([Section 5.2.3](#)).

## **5. GENERAL METHODOLOGY AND CONVENTIONS**

### **5.1. General Methods**

All confidence intervals (CIs) for proportions will be 2-sided 95% intervals, obtained using the exact Clopper-Pearson method, as described by Agresti.

The standardized asymptotic 95% CI for the difference in proportions will use the Miettinen and Nurminen method, which is described by Miettinen and Nurminen and by Newcombe.

The following decimal description will be used for the demography, reactogenicity, immunogenicity, and persistence analyses.

**Table 3. Description of Parameters**

Display Table	Parameters	Number of Decimal Digits
Demographic characteristics	Mean, median age	1
Demographic characteristics	SD (age)	1
rSBA-MenA	GMT	1
rSBA-MenC	GMT	1
rSBA-MenW-135	GMT	1
rSBA-MenY	GMT	1
Immunogenicity	Ratio of GMT	2
All summaries	% of count, including LL & UL of CI	1
All summaries	% of difference, including LL & UL of CI	2

Abbreviations: GMT = geometric mean titer; LL = lower limit of the confidence interval; rSBA-MenA, rSBA-MenC, rSBA-MenW-135, and rSBA-MenY = serum bactericidal assay using rabbit complement to measure activity against *Neisseria meningitidis* group A, group C, group W-135, and group Y; UL = upper limit of the confidence interval.

**5.2. Methods for Immunogenicity**

GMTs and GMCs will be obtained by log transformations of indicated values, averaging the log values, then exponentiating the result. The 2-sided 95% CI will be obtained by calculating the CI in log scale, referencing the t-distribution, and then exponentiating the lower and upper limits.

The day of booster vaccination will be labeled Day 0.

**5.2.1. Within Group Immunogenicity Methods**

For each group, at each blood sampling time point (Month 120 and Month 121), for each antigen assessed:

- Percentage of subjects with rSBA booster response with 95% CIs will be calculated.
- GMTs/GMCs with 95% CIs will be tabulated.
- Percentages of subjects with titers/concentrations above proposed cutoffs and with 95% CIs will be calculated.
- The antibody titers/concentrations will be tabulated and also presented using reverse cumulative distribution curves.

090177e19088d171\Approved\Approved On: 11-Mar-2019 09:48 (GMT)

CCI [Redacted]

[Redacted]

[Redacted]

[Redacted]

[Redacted]

[Redacted]

[Redacted]

CCI [Redacted]

[Redacted]

CCI [Redacted]

[Redacted]

[Redacted]

[Redacted]

[Redacted]

[Redacted]

[Redacted]

090177e19088d171\Approved\Approved On: 11-Mar-2019 09:48 (GMT)

CCI  
[Redacted text block]

**5.3. Methods for Solicited Events and Unsolicited AEs**

**5.3.1. Solicited Local And General Events (Within 4 Days Of Vaccination)**

Solicited local and general events from Days 0-3 will be recorded on diary cards.

The percentage of subjects reporting each individual solicited local (any grade, Grade 3, medical advice) and general (any grade, Grade 3, related, Grade 3 and related, medical advice) event during the 4-day follow-up period (Days 0-3) after vaccination and its exact 95% CI will be tabulated. Occurrence of fever will also be reported per temperature Grade 0,1, 2, and 3 as well as the percentage of subjects with oral temperature reported by cumulative 0.5°C increment.

The proportions of subjects reporting injection site redness >50 mm and the proportions of subjects reporting injection site swelling >50 mm will also be compiled.

Per Section 8.2.3 of the protocol, “Fever is defined as temperature  $\geq 37.5^{\circ}\text{C}$  for oral, axillary or tympanic route, or  $\geq 38.0^{\circ}\text{C}$  for rectal route. The preferred route for recording temperature in this study will be oral”.

090177e19088d171\Approved\Approved On: 11-Mar-2019 09:48 (GMT)

**5.3.2. Solicited Events and Unsolicited AEs (Within 4 Days of Vaccination)**

The percentage of subjects with at least 1 local event (solicited event and unsolicited AE), with at least 1 general event (solicited event and unsolicited AE), and with any event (solicited and unsolicited) during the 4-day (Days 0-3) follow-up period will be tabulated with exact 95% CI.

**5.3.3. Unsolicited AEs (Within 31 Days Of Vaccination)**

The percentage of subjects with unsolicited AEs within 31 days after booster vaccination (Days 0-30) and the exact 95% CI will be tabulated by vaccine group and by the Medical Dictionary for Regulatory Activities (MedDRA) preferred term. Similar tabulations will be done for Grade 3 unsolicited AEs, for unsolicited AEs possibly related to vaccination, and for Grade 3 unsolicited AEs possibly related to vaccination. For any given unsolicited AEs, the unrestricted, Grade 3, and related AEs analyses will use the same tier methodology.

SAEs (including cases of meningococcal disease and GBS) and NOCIs within 31 days following the booster vaccination will be assessed with exact 95% CI.

Pregnancies occurring within 31 days following the booster vaccination will be listed, as well as AEs/SAEs leading to withdrawal, SAEs related to study vaccination or any event related to lack of vaccine efficacy, and SAEs related to study participation.

**5.3.4. Unsolicited SAEs**

The percentage of subjects with SAEs related to primary vaccination and any event related to lack of vaccine efficacy from the subject's last visit in the primary study MenACWY-TT-036 or in the persistence study MenACWY-TT-043 EXT:036 Y2, 3, 4, 5 until entry in Study C0921005 (MenACWY-TT-101 EXT:036 Y10) and the exact 95% CI will be tabulated by vaccine group.

**5.4. Methods for Baseline Characteristics**

Summary statistics will be compiled for sex, race, age at booster vaccination, age at primary vaccination, and elapsed years from primary vaccination to booster vaccination. Sex and race will be summarized with frequency counts. Ages and elapsed years will be summarized by sample size, mean, standard deviation, minimum, and maximum. No statistical tests will be performed. Subject date of birth, sex, and race information were captured in primary study MenACWY-TT-036 database.

Frequency counts and proportions will be compiled by vaccine group for number of subjects returning at Month 120 visit, number of subjects receiving booster vaccination, number of subjects completed, and number of subjects withdrawn. The reasons for withdrawal will also be summarized.

The vaccine group sample sizes for the total cohort at Month 120 will be reconciled to the sample sizes for the ATP cohort for persistence at Month 120 by:

- Tabulating sample sizes for total cohort at Month 120.
- Tabulating sample sizes for ATP cohort for persistence at Month 120.
- Tabulating the sample sizes of reasons that subjects who are in total cohort are excluded from ATP cohort.

The vaccine group sample sizes for the booster TVC cohort will be reconciled to the booster ATP cohort for safety in the same way. The vaccine group sample sizes for the booster ATP cohort for safety will then be reconciled to the booster ATP cohort for immunogenicity.

Demographics summary will be generated on ATP cohort for persistence at Month 120, booster TVC cohort and Booster ATP cohort for immunogenicity.

## **5.5. Methods to Manage Missing Data**

### **5.5.1. Immunogenicity**

Missing immunogenicity data will be retained as missing. Meningococcal antibody titers and tetanus toxoid antibody concentrations below the cutoff will be set to 0.5\*cutoff before performing GMT/GMC calculations. The cutoff for each of the 4 meningococcal rSBAs is 1:8. The cutoff for the tetanus assay is 0.1 IU/mL.

Titers from blood samples exposed to temperature excursions may be excluded from the analysis. Determinations of exclusions will be on a case-by-case basis.

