10.5. Derived and transformed data

10.5.1. Immunogenicity

- For a given subject and a given immunogenicity measurement, missing or non-evaluatable measurements will not be replaced. Therefore, an analysis will exclude subjects with missing or non-evaluatable measurements.
- The cut-off value is defined by the laboratory before the analysis and is described in [Section 5.7.3](#).
- A seronegative subject is a subject whose titre is below the cut-off value.
- A seropositive subject is a subject whose titre is greater than or equal to the cut-off value.
- The GMTs/GMCs calculations are performed by taking the anti-log of the mean of the log titre/concentration transformations. Antibody titres/concentrations below the cut-off value of the assay will be given an arbitrary value of half the cut-off value for the purpose of GMT/GMC calculation.
- rSBA booster response for serogroups A, C, W-135 and Y after the vaccine dose is defined as:
 - For initially seronegative subjects (pre-vaccination titer below the cut-off of 1:8): rSBA antibody titers post-vaccination titer \geq 1:32 one month after vaccination, and
 - For initially seropositive subjects (pre-vaccination titer \geq 1:8): rSBA antibody titers at least four times the pre-vaccination antibody titers, one month after vaccination.
- Handling of missing data: for a given subject and a given immunogenicity measurement, missing or non-evaluatable measurements will not be replaced.

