10.6.2. Analysis of post-booster immunogenicity

The analysis of post-booster immunogenicity will be based on the Booster ATP cohort for immunogenicity. If, for any group, the percentage of subjects who come back with serological results excluded from the Booster ATP cohort is higher than 5%, a second analysis based on the Booster Total Vaccinated cohort will be performed to complement the ATP analysis.

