**6.1. Immunogenicity Endpoints**

**6.1.1. Primary Endpoints**

The primary endpoint is the booster vaccination response. The primary analysis for this endpoint will use the booster ATP cohort for immunogenicity. For any group, if more than 5% of subjects who have serological results are excluded from the Booster ATP cohort, a second analysis based on the booster TVC will be performed as a sensitivity analysis. Proportions and their 2-sided 95% CIs will be compiled for each meningococcal group.

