**6.4. Baseline and Other Summaries and Analyses**

The descriptive summary for sex, race, and age will be presented by total cohort Month 120, ATP cohort for persistence at Month 120, booster TVC, and booster ATP cohort for immunogenicity populations. Subject’s date of birth, sex, and race information will be from primary study MenACWY-TT-036 or MenACWY-TT-043.

The analyses for study conduct and subject disposition are presented below:

- Number of subjects with booster vaccination, number of subjects completed study, and number of subjects withdrawn in total cohort at Month 120.
- Number of subjects in total cohort at Month 120, number of subjects in ATP cohort for persistence at Month 120, and number of subjects with reason(s) for exclusion from ATP cohort for persistence at Month 120.
- Number of subjects in booster TVC, number of subjects in booster ATP cohort for safety, number of subjects with reason(s) for exclusion from booster ATP cohort for safety, number of subjects in booster ATP cohort for immunogenicity, and number of subjects with reason(s) for exclusion from booster ATP cohort for immunogenicity.
- Number and proportion of subjects returning diary cards in booster TVC.

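### Does case-by-case exclusion of titres from temperature-excursion samples leave the primary booster-response percentage exposed to an unmeasured shift?

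*SAP*

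**What the plan says.** SAP 5.5.1 keeps missing immunogenicity data as missing and adds: "Titers from blood samples exposed to temperature excursions may be excluded from the analysis. Determinations of exclusions will be on a case-by-case basis". Protocol 10.5.1 does not replace missing or non-evaluable measurements, and continues: "Therefore, an analysis will exclude subjects with missing or non-evaluatable measurements".

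Four other provisions decide what happens to a subject who loses a titre:

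- **Booster ATP cohort for immunogenicity (SAP 4.3).** On serology it asks only for subjects "who have assay results available for antibodies against any study vaccine antigen" in the Month 121 sample.
- **Booster ATP cohort for safety (SAP 4.2), on which 4.3 builds.** Exclusion from the Month 120 persistence cohort does not carry over when the reason was "a lack of availability of immunogenicity results at Month 120 (prebooster vaccination").
- **Second analysis.** SAP 6.1.1 runs booster response on the booster TVC "if more than 5% of subjects who have serological results are excluded from the Booster ATP cohort". Protocol 10.6.2 has the same rule, worded as when "the percentage of subjects who come back with serological results excluded from the Booster ATP cohort is higher than 5" per cent. SAP Table 4 lists the TVC analysis without that condition.
- **Booster TVC for immunogenicity (SAP 4.1).** It "will include all subjects for whom data concerning immunogenicity endpoint measures after the booster vaccination are available".

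For reporting, SAP 6.4 tabulates the "number of subjects with reason(s) for exclusion from booster ATP cohort for immunogenicity", with matching counts for the Month 120 persistence cohort. Protocol 6.5.2 and SAP 4.6 set the list of reasons for ATP elimination at data cleaning. Protocol 5.6.12 and 5.7 send sample handling, storage and shipment to the Study Procedures Manual (SPM), which is not among the documents.

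**The concern.** The rule reaches titres that have already been measured, the study is open, and nothing says the decision is made without sight of the titre or the group. Booster response needs a pre-booster and a post-booster titre, so losing either one makes the endpoint missing.

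The existing safeguard does not fully cover this. If only the Month 120 titre is dropped, the subject stays in the booster ATP cohort but leaves the booster-response calculation, and the 5% trigger does not count the loss. If the TVC analysis is run, the documents do not say whether it takes the titre back.

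At stake is the primary result itself: a within-group percentage with an exact interval, from about 135 and 45 subjects. If titres were judged after the results were known, the percentage could move, and no table is expressly planned to show it with those titres kept.

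**Working it through.** **1. The plan's own precision figures.** Protocol 10.3 expects 200 × 0.9 = 180 evaluable subjects: 150 × 0.9 = 135 and 50 × 0.9 = 45. Clopper-Pearson limits at x = N × p, rounded to the nearest integer, reproduce all 18 intervals in protocol Table 17. For example, 122/135 gives 84.1 to 94.8, and 36/45 gives 65.4 to 90.4.

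**2. Where a dropped titre goes.**

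| What is dropped | Stays in booster ATP cohort? | Has a booster-response result? | Where the loss is visible |
|---|---|---|---|
| Month 120 sample, all antigens | Yes (SAP 4.2 exception, SAP 4.3) | No | Reason counts for the persistence cohort, since SAP 4.5 needs at least one Month 120 result |
| Some serogroups only, either visit | Yes | No, for those serogroups | Smaller denominator for those serogroups |
| Month 121 sample, all antigens | No (SAP 4.3) | No | Reason counts for the booster ATP cohort |

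The gap in the 5% trigger is therefore real for the first two rows. Even so, whole-sample losses at either visit appear in a planned table of exclusion reasons, and partial losses show in the denominators.

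**3. Largest possible shift, as an illustration.** The documents give no excursion rate. Assume k = 6 of 135 and k = 2 of 45 (4.4% each), the most that do not exceed 5%. With x responders among n, the percentage ranges from (x − k)/(n − k), if all dropped are responders, to x/(n − k), if all are non-responders. The baselines are the 80% and 90% rows of Table 17.

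| Group | Titres kept (95% CI) | All dropped are responders | All dropped are non-responders |
|---|---|---|---|
| ACWY-TT | 108/135 = 80.0% (72.3–86.4) | 102/129 = 79.1% | 108/129 = 83.7% |
| ACWY-TT | 122/135 = 90.4% (84.1–94.8) | 116/129 = 89.9% | 122/129 = 94.6% |
| MenPS | 36/45 = 80.0% (65.4–90.4) | 34/43 = 79.1% | 36/43 = 83.7% |
| MenPS | 41/45 = 91.1% (78.8–97.5) | 39/43 = 90.7% | 41/43 = 95.3% |

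Every shifted value lies inside the interval calculated with the titres kept.

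**4. How likely the upper ends are if exclusion is unrelated to response.** The chance that all k dropped are non-responders is C(n − x, k)/C(n, k):

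- ACWY-TT, 90%: C(13,6)/C(135,6) = 1,716/7,511,839,335, about 2 in 10 million.
- ACWY-TT, 80%: C(27,6)/C(135,6) = 296,010/7,511,839,335, about 4 in 100,000.
- MenPS, 90%: C(4,2)/C(45,2) = 6/990 = 0.6%.
- MenPS, 80%: C(9,2)/C(45,2) = 36/990 = 3.6%.

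**5. Typical shift under the same assumption.** The mean shift is zero. With p = x/n and m = n − k, its standard deviation is √[p(1 − p)/m × k/(n − 1)]:

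- ACWY-TT, 80%: √[0.16/129 × 6/134] = 0.7 points.
- MenPS, 80%: √[0.16/43 × 2/44] = 1.3 points.

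**6. Limit of the illustration.** The 5% trigger does not cap Month 120 losses, so 6 and 2 are not upper bounds. With 13 of 135 dropped at the 80% baseline, all non-responders, the figure is 108/122 = 88.5%, above the 86.4 limit. That would take both many excursions and complete selection on response, and the documents point to neither.

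**The case for a change.** The strongest case for acting is that discretion over measured results in an open study should be closed in advance, and that doing so costs a few sentences and one extra run of an existing table. The data-cleaning provision concerns the elimination of subjects from ATP cohorts, not individual titres, and it requires no masking. If the SPM holds an excursion criterion, SAP 5.5.1 does not cite it. Descriptive analysis is no full answer either, because the percentage and its interval are the whole primary result.

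Much of this stands as description. The criterion and masking are unstated, and a lost Month 120 titre does bypass the 5% trigger. What does not stand is the step to a defect in the plan:

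- TVC handling of these titres is unspecified, not ruled out. SAP 5.5.1 does not say which analysis it means, and a measured titre can be read as available under SAP 4.1.
- Protocol 5.6.12.1 sets serum storage at −20°C or below, and SAP 4.3 requires compliance with protocol procedures. A storage breach can therefore also be read as an ATP elimination, which would be counted and tabulated.
- Widening the 5% trigger gains nothing if the TVC analysis then lacks the same titre.
- Removing non-evaluable measurements is what protocol 10.5.1 prescribes. If warming lowers a titre (an assumption), a degraded pre-booster sample overstates the rise and a degraded post-booster sample understates it. Exclusion then removes error.

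**Conclusion.** The concern does not call for a change. SAP 5.5.1 leaves a routine sample-quality decision to be made when an excursion occurs, and an analyst applying ordinary laboratory judgement, from how the sample was stored and shipped, reaches a sound result under the text as written. No stated rule or figure is wrong.

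The actual effect is unknown. It is nil if no excursion occurs and nil on average if exclusions are unrelated to response. The shift of about 4 points requires 6 of 135 or 2 of 45 to be dropped with every one a non-responder, and it leaves the estimate inside the interval calculated with all titres kept. The visible part of protocol 10.7 describes the analyses as descriptive, and no threshold or margin appears for such a shift to cross.

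This rests on three assumptions: exclusions follow the condition of the sample and not the titre; excursions are few; and the SPM, which could not be read, governs sample handling as the protocol says. Evidence of many excursions, or of exclusions made with the titres in view, would reopen the question.
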